##### [10] Hepatitis B virus test (HBs antigen, HBs antibody, and HBc antibody)

The results of tests within 3 months prior to the start of treatment should be recorded.

##### [11] Laboratory tests (peripheral leukocyte count, peripheral lymphocyte count, $\beta$ -D-glucan)

2) Survey form

(1) Patient characteristics prior to and at the start of treatment

The following will be recorded for both treatment groups.

[1] Height/weight

[2] Inpatient/outpatient status

Indication (Patients with rheumatoid arthritis), stage and grade (Steinbrocker stage), and functional class (Steinbrocker functional class)

[3] Duration of disease

[4] Clinical history (past history and concurrent illness)

[5] History of smoking (history of smoking at treatment start)

[6] Family history of malignant tumor

(2) Previous treatment drugs for rheumatoid arthritis (3 months before treatment start)

The following will be recorded for both treatment groups.

[1] MTX

- Past use (presence/absence)
- Weekly dosage
- Duration of treatment

[2] Oral steroid use for rheumatoid arthritis

- Past use (presence/absence), period or treatment

[3] Tacrolimus

- Past use (presence/absence)
- Duration of treatment

(3) Dose record

[1] Xeljanz group

Number of doses per day, treatment period, reason for change (if there has been a change in administration)

[2] Control group

If there has been a switch to another type of pharmacotherapy, excluding Xeljanz, during the observation period, the case will be handled as a continued surveillance case, and the treatment record should be continuously entered.

In cases where Xeljanz has been administered, surveillance as a member of the control group will be handled as discontinued, and registration in the Xeljanz group will be necessary.

● MTX

Name of drug (name of product), weekly dosage, and duration of treatment

● Pharmacotherapy with drugs other than MTX (biological preparation, DMARDs, immunosuppressants, oral steroid preparations)

Name of drug (name of product), daily dosage (oral steroids), and duration of treatment

(4) Concomitant therapy (Xeljanz group)

For drug therapy, covering the period starting 3 months prior to the start of treatment in this Surveillance

and ending at the completion or discontinuation of the observation period will be completed. Medications used for the treatment of adverse events should also be recorded.

[Concomitant therapies coadministered with Xeljanz]

- [1] MTX
- [2] Biological preparations\*
- [3] DMARDs other than MTX and immunosuppressants\*
- [4] Oral steroid
- [5] Other drugs

Name of drug (product name), dosage (MTX, Oral steroids), duration of treatment, and reason for treatment (Other drugs)

\*Please do not coadminister biological preparations and immunosuppressants along with Xeljanz.

[Surgical treatment of rheumatoid arthritis]

Name of the surgical therapy for rheumatoid arthritis, the date of operation, and the reason for operation should be recorded.

- (5) Whether or not pneumococcus vaccine has been administered (both groups). \*Until 12 months after surveillance start in control group
- (6) Prophylactic administration to prevent tuberculosis, pneumocystis jiroveci pneumonia, and hepatitis B (nucleic acid analogs) (both groups). \*For control group, until 12 months after surveillance start

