- [3] Adverse events leading to death, course of death

Definition of [Malignant tumor]

An event to which definitive diagnosis of malignant tumor (including lymphoma) is given

\*\*"Suspected malignant tumor (including lymphoma)" should also be reported as an adverse event.

Definition of [Serious infection]

Of the infections occurred during this Surveillance, a "serious infection" is defined as an event that;

- [1] Results in or may result in death;
- [2] Results in or may result in disability/incapacity;
- [3] Requires hospitalization or prolongation of existing hospitalization; or
- [4] Is another serious event equivalent to the above.

**Note:** Adverse events are any and all untoward events (including clinically significant abnormal changes in laboratory tests) occurred in subjects after starting Xeljanz treatment regardless of their causal relationship with Xeljanz. Serious adverse events are any untoward medical occurrences that result in death, are life-threatening, require (or prolong) hospitalization, cause persistent or significant disability/incapacity, result in congenital anomalies or birth defects, or are other conditions which represent significant health hazards.

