### **5.4. Subgroups**

For the Xeljanz group, safety and efficacy will be analyzed for each of the following subgroups.

- Sex
- Age class ( $\geq 65$  years,  $< 65$  years)
- Presence or absence of hepatic dysfunction (Presence of hepatic dysfunction is defined as the item “current hepatic dysfunction” in the medical history being checked.)
- Presence or absence of renal dysfunction (Presence of renal dysfunction is defined as the item “current renal dysfunction” in the medical history being checked.)
- Average actual daily dose ( $< 7.5$  mg,  $\geq 7.5$  mg)

Patients that may be contraindicated in the package insert of Xeljanz (hereinafter referred to as contraindicated patients) are extracted based on the criteria specified separately, and a subpopulation analysis of safety is performed.

In addition, safety and efficacy will be analyzed for each of the patient background subgroups specified in Appendix 11.1.3 and 11.1.4.

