### 6.3. Covariates

For both the Xeljanz and control groups, candidate covariates related to the development of malignant tumors and serious infections are shown below.

Covariates	Malignant tumor	Serious infection
Sex	○	○
Age	○	○
Weight	○	○
Stage of rheumatoid arthritis	○	○
Class of rheumatoid arthritis	○	○
Duration or disease	○	○
Past history (infection)	×	○
Past history (malignant tumor)	○	×
Past history (lung disorder)	×	○
Past history (interstitial pneumonia)	×	○
Complication (infection)	×	○
Complication (malignant tumor)	○	×
Complication (hepatitis B)	○	×
Complication (hepatitis C)	○	×
Complication (diabetes mellitus)	×	○
Smoking history	○	○
Family history of malignant tumors (including lymphoma)	○	○
History of MTX use (Within 3 months prior to the start of survey)	○	○
MTX criteria	○	○
History of oral steroid use (Within 3 months prior to the start of survey)	○	○
History of tacrolimus use (Within 3 months prior to the start of survey)	○	○
Past use of biological agents (Within 3 months prior to the start of survey)	○	○

Covariats	Malignant tumor	Serious infection
Initial dose of Xeljanz	○	○
Neutrophil count	○	○
Lymphocyte count	○	○
Prophylactic administration to prevent tuberculosis	×	○
Prophylactic administration to prevent pneumocystis jiroveci pneumonia	×	○
Prophylactic administration to prevent hepatitis B	×	○
DAS28	○	○

○: Applicable, ×: Not applicable

Covariates may be added or removed based on the results of the interim analyses of this survey and newly obtained findings. In that case, this plan will be revised.

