## Nominal Scale

Item	Category	Note
Past history (tuberculosis-related disease)	Absent, Present	Reference: Absent
Complication (malignant tumor)	Absent, Present	Reference: Absent
Complication (autoimmune disease)	Absent, Present	Reference: Absent
Complication (Sjogren's syndrome)	Absent, Present	Reference: Absent
Complication (cardiovascular disease)	Absent, Present	Reference: Absent
Complication (hypertension)	Absent, Present	Reference: Absent
Complication (angina pectoris)	Absent, Present	Reference: Absent
Complication (myocardial infarction)	Absent, Present	Reference: Absent
Complication (heart failure)	Absent, Present	Reference: Absent
Complication (arrhythmia)	Absent, Present	Reference: Absent
Complication (pulmonary disorder)	Absent, Present	Reference: Absent
Complication (interstitial pneumonia)	Absent, Present	Reference: Absent
Complication (gastrointestinal disorder)	Absent, Present	Reference: Absent
Complication (diverticulum)	Absent, Present	Reference: Absent
Complication (gastrointestinal perforation)	Absent, Present	Reference: Absent
Complication (hepatic dysfunction)	Absent, Present	Reference: Absent
Complication (hepatitis B)	Absent, Present	Reference: Absent
Complication (hepatitis C)	Absent, Present	Reference: Absent
Complication (other hepatitis)	Absent, Present	Reference: Absent
Complication (hepatitis B virus carrier)	Absent, Present	Reference: Absent
Complication (hepatitis C virus carrier)	Absent, Present	Reference: Absent
Complication (other hepatitis virus carrier)	Absent, Present	Reference: Absent
Complication (renal dysfunction)	Absent, Present	Reference: Absent
Complication (metabolic abnormality)	Absent, Present	Reference: Absent
Complication (diabetes mellitus)	Absent, Present	Reference: Absent
Complication (lipid abnormality)	Absent, Present	Reference: Absent
Complication (anemia)	Absent, Present	Reference: Absent
Smoking history 1	Absent, Present	Reference: Absent

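### Inpatient status and current renal and hepatic dysfunction are recorded in both groups but are not in the SAP 6.3 covariate table, so the adjusted serious-infection hazard ratio may keep residual confounding of unknown size and direction

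*Protocol*

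**What the plan says.** **Collection.** In Protocol 7.1, survey form item (1), the list of patient characteristics opens with "The following will be recorded for both treatment groups". It includes "Inpatient/outpatient status" and clinical history, both past and concurrent.

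**Tabulation.** SAP Appendix 11.1.2 lists inpatient/outpatient status and the complications renal dysfunction and hepatic dysfunction. SAP 8.2.2 explains that complications mean current medical history. These rows do not carry the Xeljanz-only note that other rows in the same appendix carry.

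**Use within the Xeljanz group.** SAP 5.4 makes "Presence or absence of renal dysfunction" a subgroup factor, and hepatic dysfunction likewise. Appendix 11.1.3 lists both as safety background factors. SAP 8.2.3.2 tabulates serious infections, as adverse drug reactions, by the 5.4 factors.

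**Use in the group comparison.** SAP 6.3 introduces its table by saying that "candidate covariates related to the development of malignant tumors and serious infections are shown below". It marks 25 rows for serious infection. The only complications among them are infection and diabetes mellitus. There is no row for inpatient status, renal dysfunction or hepatic dysfunction.

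**Endpoint.** One criterion for a serious infection in Protocol 7.6 is "Requires hospitalization or prolongation of existing hospitalization". SAP 6.1.1 has an equivalent criterion.

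**The concern.** The comparison of serious infections with the control group is a stated objective, and the groups are not randomised. Selection also differs by design. Xeljanz registrations are checked in advance against contraindications, screening results and proper use, while control patients are chosen according to routine prescribing (Protocol 6.4 and 7.1).

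The credibility of the adjusted estimate therefore rests on the covariate list. Three baseline factors that were collected in both groups are not on it. Two of them the SAP itself treats as relevant to safety in the Xeljanz group. The third touches the endpoint definition: a patient already in hospital at start can meet the prolonged-stay criterion without a new admission. SAP 6.3 gives no reason for leaving them out, although it marks, for example, family history of malignant tumours for serious infection.

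If any of the three differs between groups after weighting and also predicts serious infection, the difference passes into the adjusted hazard ratio. The standardized differences in SAP 8.2.3.1.2 are computed for the background items used as covariates, so they would not show it.

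**Working it through.** **1. What the covariate table feeds.** For serious infection, the SAP 6.3 list supplies:
- the propensity score (8.1.6);
- the weighted hazard ratio, through that score;
- the covariate-adjusted Cox hazard ratio;
- the single-factor pooled ratios and differences;
- the before-and-after balance table (all but the first in 8.2.3.1.2).

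A factor missing from the list is missing from all of these.

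**2. Figures in the plan.** There is no serious-infection rate, no prevalence for the three factors and no risk ratio, so no plan figure bears on this point. The only event count stated is 104 malignant tumours. It reproduces: 4000 × 3 × (1 + 0.5)/2 = 9000 person-years, and 9000 × 0.0116 = 104.4. It concerns another endpoint and is not used below.

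**3. Illustrative bias from one omitted binary factor.** With no true drug effect,

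observed ratio = [1 + p1(R − 1)] / [1 + p0(R − 1)]

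where p1 is the prevalence in the Xeljanz group, p0 the prevalence in the control group after weighting, and R the risk ratio of the factor for serious infection. This approximates the hazard ratio when events are uncommon. It assumes that the listed covariates absorb none of the factor's effect. All values of p1, p0 and R are assumptions.

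Worked case, inpatients 5% vs 10%, R = 3: (1 + 0.05 × 2)/(1 + 0.10 × 2) = 1.10/1.20 = 0.917. Reversed: 1.20/1.10 = 1.091.

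| Factor (assumed p1 vs p0) | R = 1.5 | R = 2 | R = 3 |
|---|---|---|---|
| Any factor, equal prevalence | 1.00 | 1.00 | 1.00 |
| Inpatient 5% vs 10% | 0.976 | 0.955 | 0.917 |
| Inpatient 10% vs 5% | 1.024 | 1.048 | 1.091 |
| Inpatient 5% vs 20% | 0.932 | 0.875 | 0.786 |
| Inpatient 20% vs 5% | 1.073 | 1.143 | 1.273 |
| Renal or hepatic 8% vs 12% | 0.981 | 0.964 | 0.935 |
| Renal or hepatic 12% vs 8% | 1.019 | 1.037 | 1.069 |
| Renal or hepatic 5% vs 15% | 0.953 | 0.913 | 0.846 |
| Renal or hepatic 15% vs 5% | 1.049 | 1.095 | 1.182 |

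**4. Scale against random error.** Assume a serious-infection rate of 3 per 100 patient-years and 0.9 years of mean follow-up. Then 4000 and 2000 patients give 108 and 54 events. The unweighted 95% limits lie a factor exp(1.96 × √(1/108 + 1/54)) = 1.39 either side of the estimate. For assumed rates of 2 and 7 per 100 patient-years the factor is 1.49 and 1.24. A shift to 0.92 or 1.09 is well inside that. A shift to 0.79 or 1.27 is not negligible beside it.

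**The case against.** **No imbalance is shown.** A reader might infer that the adjusted hazard ratio is confounded. The documents do not support that. It would need a difference between groups that remains after conditioning on the listed covariates, and none is reported. The 25 marked rows include age, stage, functional class, oral steroids, diabetes, lung disease and infection. Functional class 4 covers patients who are largely bed-ridden, so it partly stands in for inpatient frailty. The formula above ignores such absorption and so probably overstates the bias. This stands, and it limits the claim to possible residual confounding.

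**A crude imbalance would be visible.** The background and complication tables in SAP 8.2.2 cover these items. This stands for the unweighted data. Those tables cannot show whether weighting removed an imbalance.

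**The prolonged-stay argument is limited.** A reader might infer that inpatients must reach the endpoint more often. Status is recorded once, at start, while the endpoint runs for up to one year (SAP Table 6). Prolongation can act only during the initial stay, and outpatients qualify by being admitted. The direction is therefore open.

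**Some text is redacted.** The material after SAP 8.2.3.1.3 is blacked out, and the revision history places a between-group sensitivity analysis in 8.2.3.1.4. It may use these factors. That could soften the gap, but it would not change the main covariate list.

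**The sponsor considered two of the factors.** The version 8.0 entry in the revision history mentions hepatic and renal dysfunction under 6.3. A difference between that entry and the current table is not an error. It is a reason to ask whether the rows are meant to be there.

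**The survey is exploratory (SAP 4), and covariate choice is partly judgement.** This is true, but the factors are already collected and the group comparison is a named objective.

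**Conclusion.** The omission is confirmed in the current SAP 6.3 table. The serious-infection hazard ratio may keep residual confounding from factors that were measured in both groups and not used. Its size and direction cannot be determined from the documents.

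Under the stated assumptions the ratio would read about 0.92 to 1.09 for inpatient shares of 5% and 10%, in either direction, at threefold risk. It would read 1.00 with equal shares. The widest assumed contrast, 5% against 20%, gives 0.79 or 1.27, and nothing in the documents makes that contrast likely. All of these figures assume no drug effect and no absorption by the listed covariates.

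This is worth correcting because correction is nearly free. It does not show that the comparison is invalid.

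**What to change.** In the serious-infection column of SAP 6.3, add rows for inpatient/outpatient status at start, current renal dysfunction and current hepatic dysfunction. They then enter the propensity score, the weighted and Cox models and the pooled ratios. Report their standardized differences before and after weighting. SAP 6.3 already provides for adding covariates by revising the plan.

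Version 10.0 was written after database release, and SAP 6.1.1 refers to a final analysis on the July 2021 data cutoff. The extended model should therefore be labelled a post hoc sensitivity analysis and shown beside the existing one, without replacing it. The sponsor should also confirm whether the two organ-dysfunction rows were meant to be in the current table.

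The cost is a SAP revision, a re-run and three more terms beside the 25 already marked. No new data are needed.

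Pneumococcal vaccination might seem a natural further addition, since it too is collected in both groups. Protocol 7.1 item (5) specifies only whether vaccine was given, over a period that runs past the start. Without vaccination dates it cannot be treated as a baseline covariate, and it should be left out.

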## 7.2 Tests/examinations

In Xeljanz group, enter results of tests performed from before treatment start to end of observation period or date of discontinuation.

For test/examination results, a copy of the original report may be attached; provided that personal information must be processed with masking (blackened) or other method to anonymize the data.

### 1) Clinical laboratory tests

The results of clinical laboratory to the start of treatment (within 1 month prior to the start of treatment including the date treatment is commenced) and during and until the completion/discontinuation of the observation period should be recorded. If the observation period is discontinued, the test results at the time of discontinuation should be recorded if at all possible.

- [1] Hematological test: WBC, neutrophil, lymphocyte, RBC, platelets, and hemoglobin

\*Results of tests performed prior to the start of treatment (within 1 month prior to the start of treatment including the date treatment is commenced) and at 1, 3, 6, 12, 24, and 36 months of treatment will be essential.

- [2] Chemistry: AST (GOT), ALT (GPT), AL-P, LDH, HDL-C, LDL-C,  $\gamma$ -GTP, total bilirubin, triglyceride, serum creatinine and creatine kinase

\*Results of tests performed prior to the start of treatment (within 1 month prior to the start of treatment including the date treatment is commenced) and at 1, 3, 6, 12, 24, and 36 months of treatment will be essential.

- [3] Other tests: KL-6,  $\beta$ -D-glucan, and BUN

2) Chest X-ray or CT

Tests before treatment start and 12, 24, and 36 months after treatment start are considered essential.

3) Interferon  $\gamma$  (Quantiferon test, T-SPOT test, etc.)/tuberculin reaction

Tests before treatment start are considered essential.

4) Blood pressure (systolic/diastolic)

Tests before treatment start and 6, 12, 24, and 36 months after treatment start are considered essential.

5) Hepatitis B/C virus tests (HBs antigen, HBs antibody, HBc antibody, HBV-DNA, and HCV-antibody)

Tests before treatment start are considered essential. After treatment start, indicate whether HBV-DNA tests have been performed.

6) Assessment variables

The following assessment variables [1] to [6] will be evaluated.

The observation period will be as follows. If the observation period is discontinued, the test results at the time of discontinuation should be recorded if at all possible.

- Essential assessment timepoints: Assessment performed prior to the start of treatment (within 1 month prior to the start including the date treatment is commenced) and at 6, 12, 24, and 36 months of treatment (until completion of the observation period).

[Assessment variables]

[1] Tender joint count (evaluation of 28 joints)	[2] Swollen joint count (evaluation of 28 joints)
[3] Patient-reported outcome (Patient VAS)	[4] Doctor-reported outcome (Doctor VAS)
[5] C-reactive protein (CRP)	[6] Erythrocyte sedimentation rate (ESR): 1-hour value

### 7.3 End-of-surveillance (discontinuation) record

Confirm whether or not treatment can be continued by Xeljanz or control group at end of observation period. If treatment by Xeljanz group or control group cannot be continued, write date of discontinuation and select item that corresponds to reason (multiple responses possible).

However, even if a switch to another type of pharmacotherapy, excluding Xeljanz, has been made in the control group after registration is complete, it will be handled as a continuing surveillance case, and if the pharmacotherapy has been discontinued, it will be handled as a surveillance discontinued case.

If adverse event or death is selected as the reason, the details thereof should be recorded in the adverse event section. [Also, for the control group, if the reason selected is associated with malignant tumor and death of patient (treatment start to 36 months) or serious infection (treatment start to Month 12 of treatment), the details thereof should be recorded].

 
[1] Remission
 
[2] Inadequate clinical response
 
[3] Adverse event
 
	} [1]-[3]: Subject to follow-up survey e)

 
[4] Death (date of death)
 
[5] No revisit
 
[6] Transfer to another hospital/department (name of hospital/department)
 
[7] Treatment with Xeljanz tablets (*Only applicable for the survey form for the control group)
 
	} [4]-[7]: End surveillance if any of the following apply

 
[8] Other
 
	

e) However, the observation period for subjects who correspond to "1) Xeljanz group (2) in 6.5 Observation period" will be only 6 months after the date of treatment start (Booklet 1) and no follow-up surveillance will be conducted.

#### 7.4 Effectiveness evaluation

For the Xeljanz group, the following effectiveness evaluation will be performed.

Effectiveness will be evaluated based on the results of "7.2, 6) [Assessment variables] [1] to [6]."

(1) SDAI (Simplified Disease Activity Index)

Sponsor will calculate the values based on the results of [Assessment variables] [1] to [5], and based on which, disease activities will be evaluated.

Also, Sponsor will calculate the values for CDAI (Clinical Disease Activity Index) based on the results of [Assessment variables] [1] to [4], and based on which, disease activities will be evaluated.

(2) DAS28 and the changes thereof (rate)

Sponsor will calculate the values based on the results of [Assessment variables] [1], [2], [3], and [6], and based on which, disease activities will be evaluated. In addition, changes in DAS28 (rate) prior to the start of treatment and at each assessment timepoint will be computed to evaluate the increase and decrease at each timepoint.

#### 7.5 Pregnancy status

For both treatment groups, female patients should be verified for presence/absence of pregnancy at the end of the observation period for each booklet.

